10.3.3.3 Assessment of Liver Elevations

The frequencies and percentages of subjects with post baseline liver-specific function test values that meet the following criteria of potential clinical interest will be summarized by the actual treatment received at the time of the event occurrence. Two sets of summaries, namely "summary based on all study drug exposure" and "summary based on long-term study drug," will be provided, similarly as described in Section 10.3.3.2.

- $ALT \geq 3 \times ULN$
- $ALT \geq 5 \times ULN$
- $ALT \geq 10 \times ULN$

- $ALT \geq 20 \times ULN$
- $AST \geq 3 \times ULN$
- $AST \geq 5 \times ULN$
- $AST \geq 10 \times ULN$
- $AST \geq 20 \times ULN$
- $TBL \geq 2 \times ULN$
- Alkaline phosphatase $\geq 1.5 \times ULN$
- ALT and/or AST $\geq 3 \times ULN$ and concurrent TBL $\geq 1.5 \times ULN$
- ALT and/or AST $\geq 3 \times ULN$ and concurrent TBL $\geq 2 \times ULN$

A listing of potentially clinically significant liver elevations based on criteria specified above will be provided. For each of these subjects, the whole course of the respective parameter will be listed.

10.4 Analysis of Vital Signs

10.4.1 Variables and Criteria Defining Abnormality

Vital sign variables include sitting systolic blood pressure, sitting diastolic blood pressure, pulse rate, respiratory rate, body temperature, and weight. The criteria for potentially clinically significant vital sign findings are presented in [Table 12](#).

Table 12. Criteria for Potentially Clinically Significant Vital Sign Findings

Vital Sign	Category	Criteria for Potential Clinically Significant Vital Signs
Systolic blood pressure	Low	Value \leq 90 mmHg and decrease \geq 20 mmHg from Baseline
	High	Value \geq 160 mmHg and increase \geq 20 mmHg from Baseline
Diastolic blood pressure	Low	Value \leq 50 mmHg and decrease \geq 15 mmHg from Baseline
	High	Value \geq 105 mmHg and increase \geq 15 mmHg from Baseline
Pulse	Low	Value \leq 50 bpm and decrease \geq 15 bpm from Baseline
	High	Value \geq 120 bpm and increase \geq 15 bpm from Baseline
Respiratory Rate	Low	< 10 rpm
	High	> 24 rpm
Body temperature	High	> 39.0 degrees C (102.3 degrees F)
Weight	High	> 7% increase from baseline
	Low	> 7% decrease from baseline

10.4.2 Analysis of Short-Term Vital Signs

Analyses of mean change from baseline in continuous vital sign variables which are measured longitudinally will be performed by visits and by the "as treated" treatment group. Analysis will be conducted for "safety analysis up to Week 26 censored at treatment switching." For each change from baseline analysis, the following summary statistics will be presented for each treatment group: sample size, baseline mean, visit mean, and the mean, standard deviation, and median of the changes from baseline.

The number and percentage of subjects meeting the criteria for potentially clinically significant vital sign values will be summarized by "as treated" treatment group for "safety analysis up to Week 14" and "safety analysis up to Week 26 censored at treatment switching," respectively.

10.4.3 Analysis of Long-Term Vital Signs

Analyses of mean change from baseline in continuous vital signs variables which are measured longitudinally will be performed by visits and by "as treated" treatment group sequence as described at the end of Section 10.1.3. For each change from baseline

analysis, the following summary statistics will be presented for each treatment group: sample size, baseline mean, visit mean, and the mean, standard deviation, and median of the changes from baseline.

Long-Term Vital Sign will also be summarized based on the number and percentage of subjects meeting the criteria for potentially clinically significant vital sign values and by the actual treatment received at the time of the event occurrence. Two sets of summaries, namely "summary based on all study drug exposure" and "summary based on long-term study drug," will be provided, similarly as described in Section 10.3.3.2. In the evaluation of potentially clinically significant vital sign values, the baseline value will be determined by the last non-missing measurement recorded on or before the date of the first dose of study drug in the corresponding treatment group, similarly as described in Section 10.3.3.2.

A listing of all subjects with any vital sign values meeting the criteria for potentially clinically significant vital signs will be provided. For each of these subjects, the whole course of the respective parameter will be listed.

11.0 Appendix

[Appendix A](#) OMERACT Criteria

Appendix A. OMERACT Criteria

Rheumatology Common Toxicity Criteria v.2.0 Based on Woodworth TG, et al. Standardizing assessment of adverse effects in rheumatology clinical trials II. Status of OMERACT Drug Safety Working Group May 2006: OMERACT 8. Standardizing Assessment and Reporting of Adverse Effects in Rheumatology Clinical Trials: Enabling Description of Comparative Safety Profiles for Antirheumatic Therapies				
	1 – Mild	2 – Moderate	3 – Severe	4 – Includes Life Threatening
	Asymptomatic, or transient Short duration (< 1 week) No change in life style No medication or OTC	Symptomatic Duration (1 – 2 weeks) Alter lifestyle occasionally Meds relieve. (may be prescription), Study drug continued	Prolonged symptoms, reversible, major functional impairment Prescription meds/partial relief May be hospitalized < 24 hr Temporary study drug discontinuation, or/and dose reduced	At risk of death Substantial disability, especially if permanent. Multiple meds Hospitalised > 24 hr Study drug discontinued
A. Allergic/Immunologic				
A1. Allergic reaction/hypersensitivity (includes drug fever)	Transient rash: drug fever < 38°C; transient, asymptomatic bronchospasm	Generalised urticaria responsive to meds; or drug fever > 38°C, or reversible bronchospasm	Symptomatic bronchospasm requiring meds; symptomatic urticaria persisting with meds, allergy related oedema/angioedema	Anaphylaxis, laryngeal/pharyngeal oedema, requiring resuscitation
A2. Autoimmune reaction	Serologic or other evidence of autoimmune reaction, but patient asymptomatic: all organ function normal and no treatment is required (e.g., vitiligo)	Evidence of autoimmune reaction involving a non-essential organ or functions, requiring treatment other than immunosuppressive drugs (e.g., hypothyroidism)	Reversible autoimmune reaction involving function of a major organ or toxicity requiring short term immunosuppressive treatment (e.g., transient colitis or anaemia)	Causes major organ dysfunction, or progressive, not reversible, or requires long-term administration of high dose immunosuppressive therapy
A3. Rhinitis (includes sneezing, nasal stuffiness, post-nasal discharge)	Transient, non-prescription meds relieve	Prescription med. required, slow	Corticosteroids or other prescription med. with persistent disabling symptoms such as impaired exercise tolerance	NA
A4. Serum sickness	Transient, non-prescription meds relieve	Symptomatic, slow response to meds (e.g., oral corticosteroids)	Prolonged; symptoms only partially relieved by meds; parenteral corticosteroids required	Major organ dysfunction, requires long-term high-dose immunosuppressive therapy

A5. Vasculitis	Localised, not requiring treatment; or rapid response to meds; cutaneous	Symptomatic, slow response to meds (e.g. oral corticosteroids)	Generalised, parenteral corticosteroids required or/and short duration hospitalisation	Prolonged, hospitalisation, ischemic changes, amputation
B. Cardiac				
B1. Arrhythmia	Transient, asymptomatic	Transient, but symptomatic or recurrent, responds to meds	Recurrent/persistent; maintenance prescription	Unstable, hospitalisation required, parenteral meds
B2. Cardiac function decreased	Asymptomatic decline in resting ejection fraction by > 10%, but < 20% of baseline value	Asymptomatic decline of resting ejection fraction \geq 20% of baseline value	CHF responsive to treatment	Severe or refractory CHF
B3. Edema	Asymptomatic (e.g., 1 + feet/calves), self-limited, no therapy required	Symptomatic (e.g., 2 + feet/calves), requires therapy	Symptoms limiting function (e.g., 3 + feet/calves; 2 + thighs), partial relief with treatment prolonged	Anasarca; no response to treatment
B4. Hypertension (new onset or worsening)	Asymptomatic, transient increase by > 20 mmHg (diastolic) or to > 150/100 if previously normal, no therapy required	Recurrent or persistent increase > 150/100 or by > 10 mmHg (diastolic), requiring and responding readily to treatment	Symptomatic increase > 150/100, > 20 mmHg, persistent, requiring multi agency therapy, difficult to control	Hypertensive crisis
B5. Hypotension (without underlying diagnosis)	Transient, intermittent, asymptomatic, orthostatic decrease in blood pressure > 20 mmHg	Symptomatic, without interference with function, recurrent or persistent > 20 mmHg decrease, responds to treatment	Syncope or symptomatic, interferes with function, requiring therapy and sustained medical attention, dose adjustment or drug discontinuation	Shock
B6. Myocardial ischaemia	Transient chest pain/ECG changes; rapid relief with nitro	Recurring chest pain, transient ECG ST-T changes; treatment relieves	Angina with infarction, no or minimal functional compromise, reduce dose or discontinue study drug	Acute myocardial infarction, arrhythmia or/and CHF
B7. Pericarditis/pericardial effusion	Rub heard, asymptomatic	Detectable effusion by echocardiogram, symptomatic NSAID required	Detectable on chest x-ray, dyspnoea; or pericardiocentesis; requires corticosteroids	Pulsus alternans with low cardiac output; requires surgery

B8. Phlebitis/thrombosis/Embolism (excludes injection sites)	Asymptomatic, superficial, transient, local, or no treatment required	Symptomatic, recurrent, deep vein thrombosis, no anticoagulant therapy required	Deep vein thrombosis requiring anticoagulant therapy	Pulmonary embolism
C. General (constitutional)				
C1. Fatigue/malaise (asthenia)	Increase over baseline; most usual daily functions maintained, short term	Limits daily function intermittently over time	Interferes with basic ADL, persistent	Unable to care for self, bed or wheelchair bound > 50% of day debilitating, hospitalisation
C2. Fever (pyrexia) (note: fever due to drug allergy should be coded as allergy)	Transient, few symptoms 37.7 – 38.5°C	Symptomatic, recurrent 38.6 – 39.9°C. Relieved by meds	≥ 40°C; ≤ 24 h, persistent symptoms; partial response to meds	≥ 40°C, debilitating, > 24 h, hospitalisation; no relief with meds
C3. Headache	Transient or intermittent, no meds or relieved with OTC	Persistent, recurring, non-narcotic analgesics relieve	Prolonged with limited response to narcotic medicine	Intractable, debilitating, requires parenteral meds
C4. Insomnia	Difficulty sleeping, short term, no interfering with function	Difficulty sleeping interfering with function, use of prescription med	Prolonged symptoms, with limited response to narcotic meds	Debilitating, hospitalisation; no relief with meds
C5. Rigors, chills	Asymptomatic, transient, no meds, or non-narcotic meds relieve	Symptomatic, narcotic meds relieve	Prolonged symptoms, with limited response to narcotic meds	Debilitating, hospitalisation; no relief with meds
C6. Sweating (diaphoresis)	Episodic, transient	Frequent, short term	Frequent, drenching, disabling	Dehydration, requiring IV fluids/hospitalization > 24 hrs
C7. Weight gain	5% – 9.9%	10% – 19.9%	20% – 30%	NA
C8. Weight loss	5% – 9.9%	10% – 19.9%	20% – 30%	NA
D. Dermatologic				
D1. Alopecia	Subjective, transient	Objective, fully reversible	Patchy, wig used, partly reversible	Complete, or irreversible even if patchy
D2. Bullous eruption	Localised, asymptomatic	Localised, symptomatic, requiring treatment	Generalised, responsive to treatment, reversible	Prolonged, generalised, or requiring hospitalisation for treatment

D3. Dry skin	Asymptomatic, controlled with emollients	Symptoms eventually (1 – 2 wks) controlled with emollients	Generalised, interfering with ADL > 2 wks, persistent pruritis, partially responsive to treatment	Disabling for extended period, unresponsive to ancillary therapy and requiring study drug discontinuation for relief
D4. Injection site reaction	Local erythema, pain, pruritis, < few days	Erythema, pain, oedema, may include superficial phlebitis, 1 – 2 wks	Prolonged induration, superficial ulceration; includes thrombosis	Major ulceration necrosis requiring surgery
D5. Petechiae (without vasculitis)	Few, transient asymptomatic	Dependent areas, persistent up to 2 wks	Generalised, responsive to treatment; reversible	Prolonged, irreversible, disabling
D6. Photosensitivity	Transient erythema	Painful erythema and oedema requiring topical treatment	Blistering or desquamation, requires systematic corticosteroids	Generalised exfoliation or hospitalisation
D7. Pruritis	Localised, asymptomatic, transient, local treatment	Intense, or generalised, relieved by systematic medication	Intense or generalised; poorly controlled despite treatment	Disabling, irreversible
D8. Rash (not bullous)	Erythema, scattered macular/popular eruption; pruritis transient; TOC or no meds	Diffuse macular/popular eruption or erythema with pruritus; dry desquamation; treatment required	Generalised, moist desquamation, requires systemic corticosteroids; responsive to treatment; reversible	Exfoliative or ulcerating; or requires hospitalisation; or parenteral corticosteroids
D9. Induration/fibrosis/Thickening (not sclerodermal)	Localized, high density on palpation, reversible, no effect on ADL and not disfiguring	Local areas < 50% body surface, not disfiguring, transient interference with ADL, reversible	Generalized, disfiguring, interferes with ADL, reversible	Disabling, irreversible, systemic symptoms
E. Ear/Nose/Throat				
E1. Hearing loss	Transient, intermittent, no interference with function	Symptomatic, treatment required, reversible	Interferes with function; incomplete response to treatment	Irreversible deafness
E2. Sense of smell	Slightly altered	Markedly altered	Complete loss, reversible	Complete loss, without recovery
E3. Stomatitis	Asymptomatic	Painful, multiple, can eat	Interferes with nutrition, slowly reversible	Requires enteral support; residual dysfunction
E4. Taste disturbance (dysgeusia)	Transiently altered; metallic	Persistently altered; limited effect on eating	Disabling, effect on nutrition	NA

E5. Tinnitus	Intermittent, transient, no interference with function	Requires treatment, reversible	Disabling, or associated with hearing loss	Irreversible deafness
E6. Voice changes (includes hoarseness, loss of voice, laryngitis)	Intermittent hoarseness, able to vocalise	Persistent hoarseness, able to vocalise	Whispered speech, slow return of ability to vocalise	Unable to vocalize for extended
E7. Xerostomia (dry mouth)	Transient dryness	Relief with meds	Interferes with nutrition, slowly reversible	Extended duration interference with nutrition, requires parenteral nutrition
F. Eye/Ophthalmologic				
F1. Cataract	Asymptomatic, no change in vision, non-progressive	Symptomatic, partial visual loss, progressive	Symptoms impairing function, vision loss requiring treatment, including surgery	NA
F2. Conjunctivitis	Asymptomatic, transient, rapid response to treatment	Symptomatic, responds to treatment, changes not interfering with function	Symptoms prolonged, partial response to treatment, interferes with function	NA
F3. Lacrimation increased (tearing, watery eyes)	Symptoms not requiring treatment, transient	Symptomatic, treatment required, reversible	Unresponsive to treatment with major effect on function	NA
F4. Retinopathy	Asymptomatic, non-progressive, no treatment	Reversible change in vision; readily responsive to treatment	Disabling change in vision ophthalmological findings reversible, sight improves over time	Loss of sight
F5. Vision changes (e.g., blurred, photophobia, night blindness, vitreous floaters)	Asymptomatic, transient, no treatment required	Symptomatic, vision changes not interfering with function, reversible	Symptomatic, vision changes interfering with function	Loss of sight
F6. Xerophthalmia (dry eyes)	Mild scratchiness	Symptomatic without interfering with function, requires artificial tears	Interferes with vision/function, corneal ulceration	Loss of sight

G. Gastrointestinal					
	Adequate food intake, minimal weight loss	Symptoms requiring oral nutritional supplementation	Prolonged, requiring iv support	Requires hospitalization for nutritional support	
G1. Anorexia	Asymptomatic, transient, responds to stool softener, OTC laxatives	Symptomatic, requiring prescription laxatives, reversible	Obstipation requiring medical intervention	Bowel obstruction. Surgery required	
G3. Diarrhea	Transient, increase of 2 – 3 stools/day over pre-treatment (no blood or mucus), OTC agents relieve	Symptomatic, increase 4 – 6 stools/day, nocturnal stools, cramping, requires treatment with prescription meds	Increase > 6 stools/day, associated with disabling symptoms, e.g., incontinence, severe cramping, partial response to treatment	Prolonged, dehydration, unresponsive to treatment, requires hospitalization	
G4. Dyspepsia (heartburn)	Transient, intermittent, responds to OTC antacids, H-2 blockers	Prolonged, recurrent, requires prescription meds, relieved by meds	Persistent despite treatment, interferes with function, associated with GI bleeding	NA	
G5. GI bleed (gastritis, gastric or duodenal ulcer diagnosed-define aetiology)	Asymptomatic, endoscopic finding, haemocult + stools, no transfusion, responds rapidly to treatment	Symptomatic, transfusion ≤ 2 units needed; responds to treatment	Haematemesis, transfusion 3 – 4 units, prolonged interference with function	Recurrent, transfusion > 4 units, perforation, requiring surgery, hospitalisation	
G6. Haematochezia (rectal bleeding)	Haemorrhoidal, asymptomatic, no transfusion	Symptomatic, transfusion ≤ 2 units, reversible	Recurrent, transfusion > 3 – 4 units	> 4 units, hypotension, requiring hospitalization	
G7. Hepatitis	Laboratory abnormalities, asymptomatic, reversible	Symptomatic laboratory abnormalities, not interfering with function, slowly reversible	Laboratory abnormalities persistent > 2 wks, symptoms interfere with function	Progressive, hepato-renal, anasarca, pre-coma or coma	
G8. Nausea, or nausea/vomiting (use diagnostic term)	Transient, intermittent, minimal interference with intake, rapid response to meds	Persistent, recurrent, requires prescription meds, intake maintained	Prolonged, interferes with daily function and nutritional intake, periodic iv fluids	Hypotensive, hospitalization, parenteral nutrition, unresponsive to out-patient management	
G9. Pancreatitis	Anylase elevation, intermittent nausea/vomiting, transient, responds rapidly to treatment	Anylase elevation with abdominal pain, nausea, occasional vomiting, responsive to treatment	Severe, persistent abdominal pain with pancreatic enzyme elevation, incomplete or slow response to treatment	Complicated by shock, haemorrhage (acute circulatory failure)	

G10. Proctitis	Perianal pruritus, haemorrhoids (new onset), transient, or intermittent, relieved by OTC meds	Tenesmus or ulcerations, anal fissure, responsive to treatment, minimal interference with function	Unresponsive to treatment, marked interference with function	Mucosal necrosis with haemorrhage, infection, surgery required
H. Musculoskeletal				
H1. Avascular necrosis	Asymptomatic MRI changes, non-progressive	MRI changes and symptoms responsive to rest and analgesia	MRI changes, symptoms requiring surgical intervention	Wheelchair bound; surgical repair not possible
H2. Arthralgia	Intermittent transient symptoms, no meds or relieved by OTC meds	Persistent or recurrent symptoms, resolve with meds, little effect on function	Severe symptoms despite meds impairs function	Debilitating, hospitalisation required for treatment
H3. Leg cramps	Transient, intermittent, does not interfere with function	Recurrent symptoms, minimally interferes with function or sleep, responds to meds	Persistent, prolonged interference with function or sleep, partial or no response to meds	NA
H4. Myalgia	Occasional; does not interfere with function	Frequent, requires meds (non-narcotic); minor effects on function	Major change in function/lifestyle, narcotic pain meds	Debilitating, profound weakness, requires wheelchair, unresponsive to meds
I. Neuropsychiatric				
I1. Anxiety or Depression (mood alteration)	Symptomatic, does not interfere with function; no meds	Frequent symptoms, responds to meds; interferes with ADL at times	Persistent, prolonged symptoms, partial or no response to meds, limits daily function	Suicidal ideation or danger to self
I2. Cerebrovascular ischaemia	NA	Single transient ischaemic event, responsive to treatment	Recurrent transient ischaemic events	Cerebrovascular vascular accident with permanent disability
I3. Cognitive disturbance	Subjective symptoms, transient, intermittent, not interfering with function	Objective symptoms, persisting, interferes with daily function occasionally	Persistent, or worsening objective symptoms; interferes with routine daily routine	Debilitating/disabling and permanent; toxic psychosis
I4. Depressed consciousness (somnia) (somnia)	Observed, transient, intermittent, not interfering with function	Somnia or sedation, interfering with function	Persistent, progressive, obtundation, stupor	Coma

15. Inability to concentrate	Subjective symptoms, does not interfere with function	Objective findings, interferes with function	Persistent, prolonged objective findings or organic cause	NA
16. Insomnia (in absence of pain)	Occasional difficulty sleeping, transient intermittent, not interfering with function	Recurrent difficulty sleeping; requires meds for relief; occasional interference with function	Persistent or worsening difficulty sleeping; severely interferes with routine daily function	NA
17. Libido decreased	Decrease in interest	Loss of interest; influences relationship	Persistent, prolonged interfering with relationship	NA
18. Peripheral motor neuropathy	Subjective or transient loss of deep tendon reflexes; function maintained	Objective weakness, persistent, no significant impairment of daily function	Objective weakness with substantial impairment of function	Paralysis
19. Peripheral sensory neuropathy (sensory disturbance)	Subjective symptoms without objective findings; transient, not interfering with function	Objective sensory loss, persistent, not interfering with function	Prolonged sensory loss or paraesthesias interfering with function	NA
110. Seizure	NA	Recurrence of old seizures, controlled with adjustment of medication	Recurrence/exacerbation with partial response to medication	Recurrence not controlled, requiring hospitalization; new seizures
111. Vertigo (dizziness)	Subjective symptoms, transient, intermittent, no treatment	Objective findings, recurrent, meds relieve, occasionally interfering with function	Persistent, prolonged, interfering with daily function; partial response to medication	Debilitating without response to medication, hospitalization
J. Pulmonary				
J1. Asthma	Occasional wheeze, no interference with activities	Wheezing, requires oral meds, occasional interference with function	Debilitating, requires nasal O ₂	Requires ventilator assistance
J2. Cough	Transient, intermittent, occasional OTC meds relieve	Persistent, requires narcotic or other prescription meds for relief	Recurrent, persistent coughing spasms without consistent relief by meds, interferes with function	Interferes with oxygenation; debilitating

J3. Dyspnea	Subjective, transient, no interference with function	Symptomatic, intermittent or recurring, interferes with exertional activities	Symptomatic during daily routine activities, interferes with function, treatment with intermittent nasal O ₂ relieves	Symptomatic at rest, debilitating, requires constant nasal O ₂
J4. Pleuritic pain (pleurisy)	Transient, intermittent symptoms, no treatment or OTC meds relieve	Persistent symptoms, requires prescription meds for relief	Prolonged symptoms, interferes with function, requires frequent narcotic pain relief	Debilitating, requiring hospitalisation
J5. Pneumonitis (pulmonary infiltrates)	Asymptomatic radiographic changes, transient, no treatment required	Symptomatic, persistent, requiring corticosteroids	Symptomatic, requiring treatment including O ₂	Debilitating, not reversible; or requiring assisted ventilation
J6. Pulmonary function decreased (FVC or carbon monoxide diffusion capacity – DLCO)	76% – 90% of pre-treatment value	51% – 75% of pre-treatment value	26% – 50% of pre-treatment value	≤ 25% of pre-treatment value
Laboratory Data				
K. Haematology				
K1. Hgb (g/dl) decrease from pre-treatment	1.0 – 1.4	1.5 – 2.0	2.1 – 2.9, or Hgb < 8.0, > 7.0	≥ 3.0; or Hgb < 7.0
K2. Leukopenia (total WBC) × 1000	3.0 – 3.9	2.0 – 2.9	1.0 – 1.9	< 1.0
K3. Neutropenia (× 1000)	1.5 – 1.9	1.0 – 1.4	0.5 – 0.9	< 0.5
K4. Lymphopenia (× 1000)	1.5 – 1.9	1.0 – 1.4	0.5 – 0.9	< 0.5
K5. Platelets (× 1000)	75 – LLN	50 – 74.9	20 – 49.9; platelet transfusion required	< 20; recurrent platelet transfusions

L. Chemistry					
	1.1 × ULN – 11.5	11.6 – 12.5	12.6 – 13.5; or symptoms present	> 13.5; or associated coma	
L1. Hypercalcaemia (mg/dl)	1.1 × ULN – 11.5	11.6 – 12.5	12.6 – 13.5; or symptoms present	> 13.5; or associated coma	
L2. Hyperglycemia (mg/dl) Fasting	140 – 160	161 – 250	251 – 500	> 500, or associated with ketoacidosis	
L3. Hyperkalaemia (mmol/l)***	5.5 – 5.9	6.0 – 6.4	6.5 – 7.0 or any ECG change	> 7.0 or any arrhythmia	
L5. Hypocalcaemia (mg/dl)	0.9 × LLN – 7.8	7.7 – 7.0	6.9 – 6.5; or associated with symptoms	< 6.5 or occurrence of tetany	
L6. Hypoglycemia (mg/dl)	55 – 64 (no symptoms)	40 – 54 (or symptoms present)	30 – 39 (symptoms impair function)	< 30 or coma	
L7. Hyponatraemia (mmol/l)***	-	125 – 129	120 – 124	< 120	
L8. Hypokalaemia (mg/dl)***	-	3.0 – 3.4	2.5 – 2.9	< 2.5	
L9. CPK (also if polymyositis-disease)	1.2 – 1.9 × ULN	2.0 – 4.0 × ULN	4.0 × ULN with weakness but without life-threatening signs or symptoms	> 4.0 × ULN with signs or symptoms of rhabdomyolysis or life-threatening	
L10. Serum uric acid	1.2 – 1.6 × ULN	1.7 – 2.9 × ULN	3.0 – 5.0 × ULN or gout	NA	
L11. Creatinine (mg/dl)	1.1 – 1.3 × ULN	1.4* – 1.8 × ULN	1.9 – 3.0 × ULN	> 3.0 × ULN	
L12. SGOT (AST)	1.2 – 1.5 × ULN	1.6 – 3.0 × ULN	3.1 – 8.0 × ULN	> 8.0 × ULN	
L13. SGPT (ALT)	1.2 – 1.5 × ULN	1.6 – 3.0 × ULN	3.0 – 8.0 × ULN	> 8.0 × ULN	
L14. Alkaline phosphatase	1.1 – 1.5** × ULN	1.6 – 3.0 × ULN	3.0 – 5.0 × ULN	> 5.0 × ULN	
L15. T. bilirubin	1.1 – 1.4 × ULN	1.5 – 1.9 × ULN	2.0 – 3.0 × ULN	> 3.0 × ULN	
L16. LDH	1.3 – 2.4 × ULN	2.5 – 5.0 × ULN	5.1 – 10 × ULN	> 10 × ULN	

M. Urinalysis				
	Micro only	Gross, no clots	Clots, transfusion < 2 units	Transfusion required
M1. Haematuria				
M2. Proteinuria (per 24 h)	300 – 500 mg (tr/1+)	501 – 1999 mg (2+)	2 – 5.0 g (3+) nephrotic syndrome	5.0 g (4+) anasarca
M3. WBC in urine	NA	NA	Indicating acute interstitial nephritis	Associated with acute renal failure
M4. Uric acid crystals	Present without symptoms	NA	With stones or symptoms of stones (e.g., renal colic)	Causing renal outflow obstruction and hospitalization

* In L11, 1.5 – 1.8 × ULN is changed to 1.4 – 1.8 × ULN.

** In L14, 1.1 – 2.0 × ULN is changed to 1.1 – 1.5 × ULN.

*** In L3, L7 and L8, mg/dl is changed to mmol/l.

For CPK and Creatinine NCI CTC grading will be used. For CPK therefore the following gradings apply: Grade 1: > ULN – 2.5 × ULN; Grade 2: > 2.5 – 5.0 × ULN; Grade 3: > 5.0 – 10.0 × ULN; Grade 4: > 10.0 × ULN; For Creatinine the following gradings apply: Grade 1: > 1 – 1.5 × ULN; Grade 2: > 1.5 – 3.0 × Baseline; > 3.0 – 6.0 × ULN; Grade 3: > 3.0 baseline; > 3.0 – 6.0 × ULN; Grade 4: > 6.0 × ULN.

[figure not shown]
Document Approval

Study M14465 - Statistical Analysis Plan Version 2 - 07Dec2017 (E3 16.1.9)

Version: 1.0

Date: 08-Dec-2017 10:05:42 PM

Company ID: 12082017-00F9F683B8113E-00001-en

Signed by:	Date:	Meaning Of Signature:
	07-Dec-2017 11:13:25 PM	Author
	08-Dec-2017 03:20:14 PM	Approver
	08-Dec-2017 06:20:47 PM	Approver
	08-Dec-2017 10:05:41 PM	Approver

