L8. Hypokalaemia (mg/dl)	--	3.0 – 3.4	2.5 – 2.9	< 2.5

L. Chemistry					
L9. CPK (also if polymyositis-disease)*	1.2 – 1.9 × ULN	2.0 – 4.0 × ULN	4.0 × ULN with weakness but without life-threatening signs or symptoms	> 4.0 × ULN with signs or symptoms of rhabdomyolysis or life-threatening	
L10. Serum uric acid	1.2 – 1.6 × ULN	1.7 – 2.9 × ULN	3.0 – 5.0 × ULN or gout	NA	
L11. Creatinine (mg/dl)*	1.1 – 1.3 × ULN	1.3 – 1.8 × ULN	1.9 – 3.0 × ULN	> 3.0 × ULN	
L12. SGOT (AST)	1.2 – 1.5 × ULN	1.6 – 3.0 × ULN	3.1 – 8.0 × ULN	> 8.0 × ULN	
L13. SGPT (ALT)	1.2 – 1.5 × ULN	1.6 – 3.0 × ULN	3.0 – 8.0 × ULN	> 8.0 × ULN	
L14. Alkaline phosphatase	1.1 – 2.0 × ULN	1.6 – 3.0 × ULN	3.0 – 5.0 × ULN	> 5.0 × ULN	
L15. T. bilirubin	1.1 – 1.4 × ULN	1.5 – 1.9 × ULN	2.0 – 3.0 × ULN	> 3.0 × ULN	
L16. LDH	1.3 – 2.4 × ULN	2.5 – 5.0 × ULN	5.1 – 10 × ULN	> 10 × ULN	
M. Urinalysis					
M1. Haematuria	Micro only	Gross, no clots	Clots, transfusion < 2 units	Transfusion required	
M2. Proteinuria (per 24 h)	300 – 500 mg (tr/1+)	501 – 1999 mg (2+)	2 – 5.0 g (3+) nephrotic syndrome	5.0 g (4+) anasarca	
M3. WBC in urine	NA	NA	Indicating acute interstitial nephritis	Associated with acute renal failure	
M4. Uric acid crystals	Present without symptoms	NA	With stones or symptoms of stones (e.g., renal colic)	Causing renal outflow obstruction and hospitalization	

OTC = over-the-counter medication; ADL = activities of daily living; IV = intravenous; ECG = electrocardiogram; CHF = congestive heart failure; MRI = magnetic resonance imaging; Hb = haemoglobin; LLN = lower limit of normal; ULN = upper limit of normal; WBC = white blood cells; SLE = systemic lupus erythematosus; ANA = antinuclear antibodies; H-2 blockers = histamine-2 blockers; FVC = forced vital capacity

\* For CPK and Creatinine NCI CTC grading will be used. For CPK the following gradings apply: Grade 1: > ULN – 2.5 × ULN; Grade 2: > 2.5 – 5.0 × ULN; Grade 3: > 5.0 – 10.0 × ULN; Grade 4: > 10.0 × ULN; For Creatinine the following gradings apply: Grade 1: > 1 – 1.5 × Baseline; > ULN – 1.5 × ULN; Grade 2: > 1.5 – 3.0 × Baseline; > 1.5 – 3.0 × ULN; Grade 3: > 3.0 baseline; > 3.0 – 6.0 × ULN; Grade 4: > 6.0 × ULN

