10.3.2.2 Assessment of Shift from Baseline in Clinical Laboratory Variables

The baseline and post-baseline laboratory observations will be categorized as Grade 1, Grade 2, Grade 3, and Grade 4 according to OMERACT criteria (Rheumatology Common Toxicity Criteria v.2.0). For creatine phosphokinase and creatinine, NCI CTC criteria will be used.

For each laboratory variable, shift tables will be generated that cross tabulate the subjects' as deemed appropriate by "as treated" treatment group:

- Category of the baseline value versus category of the final value.
- Category of the baseline value versus maximum category.
- Category of the baseline value versus minimum category.

Note that the minimum/maximum category is used, rather than the category of the minimum/maximum value. The two may be different due to variation in the reference range.

No statistical tests will be performed for this analysis.

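### The SAP's creatinine limits for Grades 1 and 2 do not match protocol Appendix O; read literally, they leave some values ungraded and put others in two grades

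*SAP*

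**What the plan says.** SAP section 10.3.2.2 grades laboratory values for shift tables by OMERACT, with one exception: "For creatine phosphokinase and creatinine, NCI CTC criteria will be used". Sections 10.3.2.3 and 10.3.3.2 repeat the exception for potentially clinically significant values and for the listing of Grade 3 or 4 results. None of them gives an NCI version or limits. The limits stand in the footnote that closes SAP Appendix A:

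- The lowest grade has a ULN band and nothing else: "Grade 1: > 1 – 1.5 × ULN".
- The next has one criterion of each kind: "Grade 2: > 1.5 – 3.0 × Baseline; > 3.0 – 6.0 × ULN".
- The third carries the same ULN band again: "Grade 3: > 3.0 baseline; > 3.0 – 6.0 × ULN".
- The highest is a single threshold: "Grade 4: > 6.0 × ULN".

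The footnote to protocol Appendix O has the same Grades 3 and 4 but different lower grades. For the lowest it gives "Grade 1: > 1 – 1.5 × Baseline; > ULN – 1.5 × ULN". For the one above, it differs from the SAP in the ULN band: "Grade 2: > 1.5 – 3.0 × Baseline; > 1.5 – 3.0 × ULN".

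The shift tables cross baseline grade with final, maximum and minimum grade, for example "Category of the baseline value versus maximum category".

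**The concern.** Two documents dated within a week of each other define the same grades differently, and the SAP's version is not coherent in itself. Its ULN bands jump from 1.5 to 3.0, and one band serves two grades. Protocol section 8.1 leaves full analysis detail to the SAP, so a programmer would naturally take the limits from the SAP footnote. At stake are the creatinine shift tables, which rest entirely on these grades, and to a lesser degree the Grade 3 or 4 tables and listings.

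**Working it through.** **Inputs.** Limits from the two footnotes, reading each band as above the lower and up to the upper limit:

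| Grade | SAP, × baseline | SAP, × ULN | Protocol, × baseline | Protocol, × ULN |
|---|---|---|---|---|
| 1 | none | 1 to 1.5 | 1 to 1.5 | 1 to 1.5 |
| 2 | 1.5 to 3.0 | **3.0 to 6.0** | 1.5 to 3.0 | 1.5 to 3.0 |
| 3 | over 3.0 | 3.0 to 6.0 | over 3.0 | 3.0 to 6.0 |
| 4 | none | over 6.0 | none | over 6.0 |

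Let u = value/ULN, b = baseline/ULN and r = value/baseline = u/b. Both sets were applied literally on 400 × 400 grids (160,000 points each). Where a value met several grades the highest was taken; that is an assumption. Grid shares are not shares of patients.

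**1. The gap, baseline at or below ULN.** If u > 1.5 and b ≤ 1, then r = u/b ≥ u > 1.5. The baseline criterion already gives Grade 2 or 3 in both documents. With b from 0.4 to 1.0 and u from 1.5 to 3.0, 0 of 160,000 points differ.

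**2. The gap, baseline above ULN.** A value with 1.5 < u ≤ 3.0 is ungraded in the SAP when r ≤ 1.5, that is when b ≥ u/1.5. For u = 2 this needs b ≥ 2/1.5 = 1.33. With b = 1.4 and u = 2.0, r = 1.43: no SAP grade, protocol Grade 2. With b = 1.4 and u = 2.5, r = 1.79: Grade 2 in both. With b from 1 to 2 and u from 1.5 to 3.0, 80,122 of 160,000 points (50%) fall from Grade 2 to none.

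**3. The baseline value itself.** Here r = 1, so only the ULN criterion can grade it. With b = 1.6 the baseline is ungraded in the SAP and Grade 2 in the protocol. If such a subject falls to u = 1.2, both documents give Grade 1. The protocol's table then shows Grade 2 to Grade 1, an improvement; the SAP's shows no grade to Grade 1, an apparent worsening.

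**4. The missing Grade 1 criterion.** This concerns values within ULN at more than 1 and up to 1.5 × baseline. With b = 0.7 and u = 0.8, r = 1.14: no SAP grade, protocol Grade 1. With b and u both from 0.4 to 1.0, 56,126 of 160,000 points (35%) fall from Grade 1 to none. This part can affect subjects with a normal baseline.

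**5. The overlap.** Every value with 3.0 < u ≤ 6.0 meets SAP Grades 2 and 3. With the highest grade taken, 0 of 160,000 points differ from the protocol, both for b from 0.4 to 1.0 and for b from 1 to 2. The reason is general: the Grade 3 and Grade 4 limits are identical in the two documents, so the same values meet them.

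**6. Is there a tie rule?** The maximum category in section 10.3.2.2 is taken over a subject's observations. It does not say what to do when one observation meets two grades. The protocol's limits need such a rule too: with b = 0.7 and u = 1.2, r = 1.71, so the value is Grade 1 on ULN and Grade 2 on baseline.

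**The case against.** **The mismatch may come from reading the PDF.** The text checked here was extracted by a program, and SAP Appendix A is damaged elsewhere: the anorexia row carries the constipation text and the constipation label is missing. Skipping between repeated strings could produce the SAP's Grade 1. This stands as a reason to look at the original page. It does not dispose of the point, because the Grade 3 label and both its criteria are intact after the repeated band.

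**The change may be deliberate.** The SAP marks its departures in Appendix A with asterisks (L3, L7, L8, L11 and L14), and none covers these limits. The CPK bands in the same footnote match the protocol. An unmarked change that gives one band to two grades is unlikely to be intended.

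**NCI CTC is the named standard, so the footnote need not govern.** This stands in part. Literal programming is an assumption. But the SAP gives no version and no other limits.

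A reader might infer more than the documents support:

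- *That the renal shift tables will be wrong.* That holds only if the footnote is programmed as written.
- *That Grade 3 values drop out of the potentially clinically significant table.* Section 10.3.2.3 counts subjects who meet Grade 3 or 4, and a value of 4 × ULN meets Grade 3 as written. Losing it would need a lowest-grade-first rule, which appears nowhere.
- *That surveillance of renal dysfunction as an event of special interest is compromised.* SAP Table 10 identifies those events by a narrow MedDRA query, not by creatinine grade.

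**Conclusion.** The inconsistency is real on the text as given: Grade 1 lacks a criterion, and Grade 2 carries Grade 3's ULN band. If followed literally, it under-grades two sets of values: those between 1.5 and 3.0 × ULN that are baseline values or lie at no more than 1.5 × baseline, and rises of up to 1.5 × baseline within ULN. The first set needs a baseline above ULN. Exclusion criterion 21 sets an eGFR limit but none on creatinine relative to ULN, so it does not by itself rule such baselines out; the documents give no count. Grade 3 and 4 results are unaffected provided the highest grade is used. The effect is limited to descriptive tables, for which section 10.3.2.2 plans no statistical tests. The conclusion rests on the extracted footnote being faithful to the page and on its being used as the programming source.

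**What to change.** Check the creatinine footnote on the original page of SAP Appendix A. If it reads as above, reconcile the Grade 1 and Grade 2 limits with protocol Appendix O for the laboratory shift tables and listings; if a departure is intended, mark and explain it like the others in that appendix. In either case, add one sentence stating that a value meeting more than one grade is assigned the highest. The cost is one footnote, one sentence and a check of the grading program. No data collection or patient-management rule is touched.
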